9.2.1. Inclusion Criteria

Patients must meet *all* of the following inclusion criteria to be eligible for data abstraction:

- Diagnosed with locoregional RCC (no distant metastasis at the time of diagnosis).
- Underwent a nephrectomy at Duke between 01 April 2014, and 31 December 2019 (final dates determined based on results from part 2 data collection).
- Aged 18 years or older at nephrectomy.

9.2.2. Exclusion Criteria

There are no exclusion criteria for this study.

9.3. Variables

All variables will be gathered using the DCF developed by RTI-HS and described in [Section 9.6.7](#). In the following sections, we describe the key analysis variables and study measures that will be gathered directly through the DCF or constructed during analysis. Limited data will be collected on all eligible patients with locoregional RCC nephrectomy, while additional variables will be collected for patients who are classified as having a high risk of recurrence (anticipated to be 15%-20% of the total population; see [Section 9.5](#) for details).

A small portion of patients may undergo more than one nephrectomy during the study period (anticipated to be 5%-10% of the total population). For these patients, all data will be collected in reference to the highest risk eligible tumor.

Exact dates will be collected in the DCF but will not be retained in the analytic file or transferred from Duke to RTI-HS. See [Section 10](#) for a description of the method for anonymizing date data.

9.3.1. Patient Characteristics (all eligible study patients)

Demographic characteristics available in patient medical records will be documented. The following characteristics will be included:

- Year of birth;
- Age at nephrectomy;
- Sex;
- Race and/or ethnicity.

9.3.2. Baseline Clinical Characteristics (all eligible study patients)

A number of clinical characteristics related to the initial diagnosis of locoregional RCC and nephrectomy will be collected. The following characteristics may be included (when available):

- Date of diagnosis of locoregional RCC;
- Date of nephrectomy;
- TNM [tumor, node, metastasis] stage;
- Tumor grade;
 - Fuhrman grade (I-IV);
- Tumor histology;
 - Clear cell predominant versus not clear cell predominant;
- Tumor size (cm);
- Tumor necrosis (present/absent);
- Partial versus radical nephrectomy;
- Performance status--ECOG (Eastern Cooperative Oncology Group); if a KPS (Karnofsky Performance Scale) score is abstracted, it will be converted to an ECOG score (<https://oncologypro.esmo.org/Oncology-in-Practice/Practice-Tools/Performance-Scales>).

9.3.3. Follow-up Visits (all eligible study patients)

Information about the first postoperative visit following nephrectomy will be collected for all eligible patients, when available, and any decisions regarding follow-up plans made at this visit will be documented.

- Date of first postoperative follow-up visit;
- Follow-up plan determined at first postoperative visit:
 - Surveillance;
 - Adjuvant systemic therapy;
 - Transfer of care to a non-Duke provider;
 - Follow-up plan not recorded in the medical record.

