8. RESEARCH QUESTION AND OBJECTIVES

The aim of this study is to estimate the proportion of patients diagnosed with RCC who are at high risk for recurrence following nephrectomy, describe referral patterns, and characterize treatment in this population. Exploratory analyses may include estimation of the incidence of recurrence and disease-free interval following nephrectomy, if data are available. Data for this study will be collected from a retrospective medical record review of patients diagnosed with locoregional RCC who underwent nephrectomy at Duke. The following primary objectives will be assessed:

- Describe patient demographic and clinical characteristics of patients diagnosed with locoregional RCC who underwent nephrectomy.
- Estimate the proportion of patients at high risk of recurrence following nephrectomy.

- Characterize postoperative provider referrals among patients at high risk of recurrence, including the proportion of patients who were referred to other providers and reasons for referral.
- Describe treatment characteristics following nephrectomy among patients at high risk of recurrence, including the proportion of patients who received systemic therapy, type of systemic therapy received, dose and duration of treatment, reasons for treatment discontinuation, and participation in clinical trials, where available; perform subgroup analyses to describe treatment details among the subgroup of patients receiving adjuvant systemic therapy with sunitinib.
- Estimate the incidence of disease recurrence and duration of the disease-free interval following nephrectomy among all patients at high risk of recurrence, and among the subgroup of patients receiving adjuvant systemic therapy with sunitinib.

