9.3.4. Referral Patterns (high-risk subgroup only)

Information on provider referrals for oncologic or RCC-related care will be collected only for patients at high risk of recurrence, when available.

- Dates of referral for oncologic/RCC-related care;
- Reasons for referrals for oncologic/RCC-related care;
- Referring provider type;
- Type of provider referred to;
- No documented referral for oncologic/RCC-related care.

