9.3.5. Treatment Patterns (high-risk subgroup only)

Detailed information on treatment patterns will be collected only for patients at high risk of recurrence, when available. Note that for patients participating in a competitor clinical trial, detailed information on the specific agent used will not be collected.

- Dates of subsequent surgery, procedures, and adjuvant systemic therapy;
- Type and dose of systemic agents received;
- Participation in clinical trials.

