9.7. Data Analysis

All variables described in [Section 9.3](#) will be summarized descriptively through the tabular display of mean values, 95% confidence intervals (CIs), medians, quartiles, and standard deviations of continuous variables of interest and frequency distributions for categorical variables. All open-ended text fields associated with the “other” answer option will be evaluated and described, as appropriate.

All study-eligible patients will be included in descriptive analyses of variables pertaining to patient characteristics, baseline clinical characteristics, and initial postoperative follow-up visits (see [Sections 9.3.1](#), [9.3.2](#), and [9.3.3](#) for details). Patients who are categorized as having a high risk of recurrence will be included in additional analyses described below. Risk classification will be assessed using published algorithms (eg, UISS and SSIGN score) or adaptation of a published algorithm. The primary risk classification system used to designate the high-risk subgroup for this study will be chosen based on completeness of data available in the patient medical records. Completeness will be assessed during the pilot study. If data are available to support more than one classification system, the UISS risk classification will be used. If some data are not available to support classification using a published algorithm, an adapted version of an algorithm will be explored.

Additional descriptive analyses performed within the high-risk subgroup will include referral patterns, treatment patterns, and health outcomes (see [Sections 9.3.4](#), [9.3.5](#), [9.3.6](#)). In addition to descriptive analyses, time-to-event measures (ie, time to recurrence, overall survival) will be assessed. To adjust time-to-event measures, a Kaplan-Meier method that accounts for right-censoring will be implemented (Klein and Moeschberger, 2005).⁷ To evaluate time to recurrence, the endpoint will be programmed with the date of recurrence or date of death, whichever occurs first, as an eligible event; if neither of these events occurred, the outcome will be right censored at the date of the last medical record follow-up. To evaluate overall survival, the endpoint will be programmed with the date of death as an eligible event or right censored at the date of the last medical record follow-up.

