9.9. Limitations of the Research Methods

Retrospective medical record reviews are subject to the following general limitations:

- Patients selected for study inclusion represent a sample of patients who received treatment at Duke. Therefore, study findings may not be generalizable to the overall population of patients with locoregional RCC or physicians who treat this disease in the US.
- All data captured in the DCF will be limited to information available in the patients' medical records held by Duke University. Information on health care services received outside the physician's care setting that is not recorded in the medical record will be unavailable for this study (eg, treatment received through a non-Duke urologist or other health care provider [eg, medical oncologist]).
- Data will be entered directly by the Duke research team and may be subject to entry errors and resulting inaccuracies in reporting. Although data checks will be in place to improve internal consistency of the data, responses will not be validated against the patients' medical records by an independent reviewer.

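### High-risk patients transferred to non-Duke care have no coding or denominator rule, so the systemic-therapy proportion is likely understated and the referral proportion is ambiguous

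*Combined protocol and SAP*

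**What the plan says.** Two primary objectives in section 8 are proportions among high-risk patients: "the proportion of patients who were referred to other providers and reasons for referral" and "the proportion of patients who received systemic therapy, type of systemic therapy received".

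- **Transfer.** Section 9.3.3 gives the first-visit plan four values. One is "Transfer of care to a non-Duke provider"; another is adjuvant systemic therapy.
- **Referral.** Section 9.3.4 collects "Type of provider referred to" without saying whether that provider must be inside or outside Duke. The only negative level is "No documented referral for oncologic/RCC-related care".
- **Treatment.** Section 9.3.5 says: "Detailed information on treatment patterns will be collected only for patients at high risk of recurrence, when available". It lists no level for unknown status or transferred care.
- **Analysis set.** Section 9.7 says: "Patients who are categorized as having a high risk of recurrence will be included in additional analyses described below". Section 9.2 sets no exclusion criteria and no minimum length of follow-up.
- **Limitation.** Section 9.9 says: "Information on health care services received outside the physician's care setting that is not recorded in the medical record will be unavailable for this study". It gives treatment by a non-Duke urologist or medical oncologist as an example.

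Right-censoring is specified in section 9.7 only for time to recurrence and overall survival. For the two proportions the protocol gives no denominator rule, no missing-data rule and no sensitivity analysis.

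**The concern.** The plan collects a marker for patients whose later care may not be visible and concedes the visibility problem. It then does not use the marker where it matters most. A high-risk patient sent to an outside provider and treated there, with nothing returned to the Duke record, looks the same in the tables as a patient kept at Duke and not treated.

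Section 7 says the study is meant to show whether high-risk patients reach providers who can consider adjuvant therapy, and where needs go unmet. Not treated and not observable have different meanings for that question. The coding also reaches further. Referral status and systemic treatment are candidate covariates in the Cox models of section 9.7. Part 3 was added (section 9.1.3) because referral and treatment appeared to rise from 2018 into 2019, and a transfer share that changed over time could distort that trend.

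**Working it through.** **Step 1: the plan's own denominator.** Section 9.5 expects about 650 patients, 15% to 20% of them high risk. 650 × 0.15 = 97.5, rounded up to 98; 650 × 0.20 = 130. The stated 98 to 130 is reproduced.

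**Step 2: systemic therapy.** Let t be the share of high-risk patients transferred, p_in the proportion treated among the rest, p_out the true proportion treated among those transferred, and c the share of outside treatment that reaches the Duke record.

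- True proportion = p_in(1 − t) + p_out·t
- Reported proportion, with unseen treatment counted as none = p_in(1 − t) + c·p_out·t
- Shortfall = t·p_out·(1 − c)

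The documents give none of t, p_in, p_out or c. Assume p_in = p_out = 20% and c = 0, so the true value is 20%:

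| t | Transferred, of 130 | Reported, also the worst-case bound | Shortfall | Excluding transfers | Best-case bound |
|---|---|---|---|---|---|
| 10% | 13 | 0.20 × 0.90 = 18% | 2 points | 20% | 18% + 10% = 28% |
| 20% | 26 | 0.20 × 0.80 = 16% | 4 points | 20% | 16% + 20% = 36% |
| 30% | 39 | 0.20 × 0.70 = 14% | 6 points | 20% | 14% + 30% = 44% |

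The best-case bound treats every transferred patient as having received therapy. It is a limit, not an expectation. At the lower end, 98 patients with 10% transferred means about 10 patients of unknown status.

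Over wider assumed ranges (t from 5% to 30%, p_in = p_out from 10% to 50%, c = 0) the shortfall runs from 0.05 × 0.10 = 0.5 points to 0.30 × 0.50 = 15 points. It is zero if no transferred patient is treated outside, or if all such treatment reaches the Duke record.

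**Step 3: referral.** Assume t = 20%, 30% referred among patients not transferred, and no other referral recorded for those transferred.

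- Transfer coded as no documented referral: 0.30 × 0.80 = 24%
- Transferred patients excluded: 30%
- Transfer coded as a referral: 0.24 + 0.20 = 44%

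The gap between the two codings equals t, here 20 points, whatever the referral rate among the rest. With 98 patients, 20 of them transferred, the figures are 0.30 × 78 / 98 = 23.9% and (23.4 + 20) / 98 = 44.3%.

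**The case against.** Four stronger readings are tempting, and the documents do not support them.

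- **That the plan codes transferred patients as unreferred and untreated.** A reader might infer this, but no section says it. Referral and treatment data are collected when available, and dropping such patients from a denominator is not ruled out. This objection stands as to the coding. The default remains that all high-risk patients are analysed with no level for unobserved care.
- **That the referral proportion is understated.** Section 9.3.4 does not confine referrals to Duke providers, so a transfer could itself be entered as one. A decision made by the Duke provider at or before the first visit can also be in the record; only later outside referrals are hidden. The direction is undetermined.
- **That transferred patients are wholly invisible.** Section 9.3.3 records a plan, not what followed. Section 9.9 covers only outside care that does not reach the record.
- **That patients kept at Duke should form the main estimate.** Transfer and adjuvant therapy are values of the same variable, set after the index date. Restricting to patients who stay conditions on a decision taken alongside the outcome, and could overstate treatment if those chosen for therapy tend to stay. It would also narrow the population of section 8. This objection stands in full.

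It can also be said that the study is descriptive, that section 9.9 discloses the gap, and that section 9.7 tabulates the first-visit plan for all eligible patients. That lowers the stakes. But the disclosure gives no direction of bias and no analysis, and an overall tabulation does not show how many high-risk patients without recorded therapy were transferred.

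**Conclusion.** The point holds in a limited form. The protocol defines neither the coding nor the denominator for transferred high-risk patients in two primary proportions.

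For systemic therapy, following section 9.7 as written counts unseen outside treatment as none, so the bias is downward and equals the share transferred times the proportion treated outside and not captured. A true 20% becomes 18% to 14% if 10% to 30% are transferred, treatment is equally common in both groups and nothing outside is captured. All three are assumptions, and the real size cannot be computed from the documents.

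For referral no direction can be claimed. Under the assumptions shown, an unstated convention alone moves the result between 24% and 44%. The change should be made, because it affects what the study can conclude about unmet need.

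**What to change.** In section 9.7:

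1. Keep the proportion among all high-risk patients as the main estimate for both referral and systemic therapy.
2. Report high-risk patients whose first-visit plan is "Transfer of care to a non-Duke provider" and who have no recorded systemic therapy in a separate row, labelled *care transferred, later care not observable*.
3. Add a sensitivity analysis of both proportions that excludes all patients with the transfer plan.
4. Add best- and worst-case bounds that set the unobservable patients to all and to none.

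In section 9.3.4, state whether a transfer to an outside provider counts as a referral, and apply that rule to all patients.

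The cost is a few sentences and a few table rows, using variables the study already collects. The estimate that excludes transfers may be selected, because patients kept at Duke may differ from those who leave. That is why it stays a sensitivity analysis and is shown with the bounds.

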9.3.4. Referral Patterns (high-risk subgroup only)

Information on provider referrals for oncologic or RCC-related care will be collected only for patients at high risk of recurrence, when available.

- Dates of referral for oncologic/RCC-related care;
- Reasons for referrals for oncologic/RCC-related care;
- Referring provider type;
- Type of provider referred to;
- No documented referral for oncologic/RCC-related care.

9.3.5. Treatment Patterns (high-risk subgroup only)

Detailed information on treatment patterns will be collected only for patients at high risk of recurrence, when available. Note that for patients participating in a competitor clinical trial, detailed information on the specific agent used will not be collected.

- Dates of subsequent surgery, procedures, and adjuvant systemic therapy;
- Type and dose of systemic agents received;
- Participation in clinical trials.

9.3.6. Outcomes (high-risk subgroup only)

Health outcomes will be collected only for patients at high risk of recurrence, when available.

- Date of last follow-up encounter in the medical record;
- Date of death;
- Date of disease recurrence and method of confirmation;
- Type of disease recurrence (eg, locoregional versus distant, if applicable);
- Reasons for treatment discontinuation.

9.4. Data Sources

Data will be abstracted from medical records of patients receiving care within the Duke University Health System. This study is retrospective; therefore, the collection of data will in no way influence prescribing patterns or treatment decisions.

Medical record abstractions provide a unique opportunity to collect and analyze real-world data outside the highly controlled setting of clinical trials. Generally, medical record abstraction enables collection of detailed information on patient demographic and clinical characteristics, treatment patterns, health outcomes, and health care resource utilization (HCRU) that may otherwise be unavailable in a standardized manner. The use of medical record abstraction allows for the development of a highly customized DCF that meets the specific needs of this study.

Following ethics approval, the DCF will be programmed into an Excel-based data-collection instrument. The use of an Excel-based tool not only enables streamlined abstraction but also real-time consistency checks to improve the accuracy of the recorded data. Upon finalization of the DCF, physicians at Duke will proceed with data-collection activities. Physicians will screen their patients' records to identify eligible patients. Physicians will be responsible for selecting patient medical records that meet the inclusion and exclusion criteria described in [Section 9.2](#). After the physician identifies an eligible medical record, he or she will complete the DCF for the patient by retrospectively reviewing all available data in the medical record. The use of physicians to directly abstract patient medical record data eliminates interviewer or abstractor bias. Additionally, physicians are able to quickly and accurately interpret notes contained within a patient record, thereby providing additional information from a qualitative source. See [Section 9.9](#) for a detailed review of the strengths and limitations of this study type.

9.5. Study Size

The total sample size will reflect the total number of eligible patients undergoing nephrectomy at Duke University Health System during the study period. At this time, it is estimated that this will be approximately 650 patients. Of this broader sample, it is anticipated that approximately 15%-20%, or 98-130 patients, will be classified as at high risk of recurrence and eligible for additional data collection to document treatment patterns and outcomes. As this study is exploratory in nature, no formal power calculations were conducted to determine the sample size for this study. Furthermore, this study does not

involve formal hypothesis testing and is primarily being conducted to understand clinical characteristics, treatment patterns, and health outcomes. Any significance testing will be exploratory in nature. Thus, the sample size considered for this study should be adequate to address the study objectives.

9.6. Data Management

RTI-HS will perform the analyses described in this proposal using a SAS statistical software application housed on RTI-HS's secure, large-capacity, high-performance Linux mainframe. Experienced RTI-HS programmers and analysts will perform all analyses. To ensure the integrity and quality of the study results, we will follow our programming validation life-cycle process for all analyses. This includes quality-checking programs, logs, and output for accuracy according to relevant standard operating procedures.

To ensure the integrity and quality of study results, RTI-HS implements several practice standards for statistical programming, database management, and documentation for all projects involving databases analyses. The following three steps will be undertaken to achieve this high level of quality:

- Documentation of SAS programming;
- Validation of SAS programs;
- Database storage and retention.

9.6.1. Documentation of SAS Programming

To ensure smooth transitions of analytic methods and work among programmers, reviewers, and other project personnel, documentation of the following information will be created for each SAS program:

- Project name;
- Program name;
- Program purpose;
- Program author;
- Date the program was completed;
- Descriptions of subsequent changes and/or enhancements, with name of programmer and date for each.

This information will be incorporated into each program in the form of a header. In addition to documenting this information in a general program header, each program will include

detailed comments throughout to describe the purpose and method of specific programming statements.

9.6.2. Validation of SAS Programs

In this section, we describe a variety of programming validation methods, including log review, review of data listings, and independent programming, which will be used to ensure that our SAS programs function as intended. The validation methods described in this section are not exhaustive, and additional measures will be implemented as appropriate.

